PROTOCOL TITLE: Does the VerTouch Device Improve Insertion Site Identification for Lumbar Neuraxial Procedures when Compared to Palpation or Ultrasound Guided Site Selection? A Prospective Randomized Controlled Trial

PRINCIPAL INVESTIGATOR:

[name].
Department of Anesthesiology
[contact]
[contact]

VERSION DATE: 1.1 03/26/2021

STUDY SUMMARY:

Investigational Agent(s) (Drugs or Devices)	Intuitap VerTouch Device
IND / IDE / HDE #	
Indicate Special Population(s)	Children Children who are wards of the state Adults Unable to Consent Cognitively Impaired Adults Neonates of Uncertain Viability  Pregnant Women Prisoners (or other detained/paroled individuals) Students/Employees
Sample Size	120
Funding Source	Intuitap Medical
Indicate the type of consent to be obtained	 Written Verbal/Waiver of Documentation of Informed Consent Waiver of HIPAA Authorization Waiver/Alteration of Consent Process
Site	Lead Site (For A Multiple Site Research Study) Data Coordinating Center (DCC)
Research Related Radiation Exposure	Yes  No
DSMB / DMC / IDMC	Yes  No

OBJECTIVES:

Is there an identifiable difference in the number of insertions and redirections of the needle for a lumbar neuraxial procedure when the VerTouch device is used, instead of palpation (current gold standard) or ultrasound guidance (US), for the identification of the procedural insertion site?

Null Hypothesis:

There is no difference in the number of insertions and redirections of the needle for a lumbar neuraxial procedure when the VerTouch device is used.

BACKGROUND:

Literature:

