In this project we aim to compare the VerTouch device to palpation and US techniques used to identifying the anatomic landmarks and optimal location for neuraxial access. In a previous feasibility study completed here at Northwestern University (NU) in Prentice Women's hospital (stu#: 00207454), the researchers showed that when VerTouch was used to mark a site prior to the neuraxial procedure, and the site marked was eventually used for the procedure, the success rate of the procedure with minimal needle manipulation was greater than historical data for the gold standard palpation technique. Additionally, the provider confidence in the information provided by the device was greater than 95% (abstract and/or submitted manuscript for this study can be provided on request). The proposed RCT herein will be a prospective comparison

of the now proven VerTouch device to the gold standard of palpation and the commonly cited US techniques.

SIGNIFICANCE:

Thousands of neuraxial procedures are completed daily with over 12,000 done at Prentice Women's hospital last year. These procedures are not without difficulty and complication. The gold standard of palpation and blind advancement of the needle toward the spine can result in multiple insertions of the needle into the skin and redirections of the trajectory of that needle after insertion to avoid the bones of the spine protecting the spinal column. These insertions and redirections are not only time consuming while the patient is in an uncommon position, but they also cause discomfort and possibly lasting pain days after the procedure. In addition to the patient dynamics, when anatomical or positioning issues result in difficult neuraxial procedures the common teaching is to attempt US guided access. Unfortunately, not many proceduralist are trained in this modality and the additional materials needed to perform the procedure with US take time to gather and further prolong the procedure. Additionally, though the cost of US technology is getting more reasonable, it is still rather expensive and a barrier to utilization by many facilities around the country and the world. Often, after many attempts, the proceduralist accepts failure of the procedure and refers the patient to the interventional radiology (IR) or pain medicine specialist for completion of the procedure using radiation to visualize the spine. Note, this is not an option for pregnant women who are not eligible for radiation due to fetal concerns.

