The VerTouch offers a non-invasive, untethered, and non-radiation producing device that allows for the visualization of the underlying structures of the spine to determine ideal needle placement for neuraxial procedures. The output on the screen can also be visualized by other providers or senior proceduralist for assistance with best course of action for the procedure. The device does not cause discomfort to the patient and does not require any additional materials to be functional.

This study has the potential to show that the VerTouch is more effective than palpation and as effective as US at defining the location for neuraxial procedure initiation and eventual success. If the VerTouch device is capable of improving the consistency of success of neuraxial procedures, while minimizing need for costly and cumbersome US technology and decreasing referral to radiation requiring procedures, the benefit to patients and proceduralists would be exponential.

STUDY ENDPOINTS: The primary endpoint is the combined total number of insertions or redirection of the needle being used for the procedure.

The endpoint is when all the subjects for each arm have been recruited and completed study procedures.

STUDY INTERVENTION(S) / INVESTIGATIONAL AGENT(S):

We will use the VerTouch device which we have shown to be a non-significant risk device (IDE). It is comprised of a non-invasive pressure sensor that is gently pushed against the back, with a screen that reads out the pressure being applied across the device. Areas of higher pressure are suggestive of bony areas, whereas areas of lower pressure are more likely tissue. The application of the device to the body is less obtrusive than ultrasound, which is commonly used, because this device does not use any gel or other medium.

The device will be stored in a locked space only accessible to the proceduralist or research personnel authorized to prepare the device for use. The device is self-contained and powered by an internal rechargeable battery. The device will only be at the bedside for those subjects that

have been recruited to participate. In order to maintain blinding, even if the device is not used for the recruited patient it will be at the bedside to ensure the observers are not un-blinded.

PROCEDURES INVOLVED:

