Group #3: Control group, palpation utilized for identification of site for labor epidural or spinal anesthesia procedure

Group #4: VerTouch utilized for identification of site for lumbar puncture procedure

Group #5: Ultrasound (US) utilized for identification of site for lumbar puncture procedure

Group #6: Control group, palpation utilized for identification of site for lumbar puncture procedure

Participants will be randomized to treatment groups based on a random computer-generated schedule (<https://www.randomizer.org>). Proceduralists will not be blinded to randomization, however blinded research personnel will observe the procedure after site determination and collect all outcome measures in this study.

For groups 1-3, on request of neuraxial procedure the research nurse and proceduralist will proceed to the patient's room with all normal supplies in addition to the VerTouch and US machine designated for this study. The research nurse will then un-blind to proceduralist to the patient's group and site identification will proceed. Regardless of the group, the proceduralist will make a mark at the site identified for the procedure using a chlorhexidine safe surgical marking pen. After completion of marking, the research nurse will notify the observer that they may enter the room to observe the procedure and collect the relevant data. Observers will be limited to 3 observers, and additionally inter-observer variability will be minimized using video corroboration of at least 10 procedures.

If one of the blinded study observers is not readily available due clinical responsibilities, the research nurse will video record the procedure per protocol. The procedure video will be reviewed by the blinded observer and the number of redirections and reinsertions will be counted and relayed to the research nurse for completion of data collection.

For groups 4-6, once the patient is in the procedural suite the proceduralist will be un-blinded. He/she will proceed to mark the patient with the appropriate modality determined by the group number. After marking, the proceduralist will allow the research observer to enter the room to observe the procedure and collect the relevant data. Observers will be limited to 3 observers, and additionally inter-observer variability will be minimized using video corroboration of at least 10 procedures.

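### The video fallback is told to count reinsertions while the primary endpoint counts insertions; read literally, a video-scored patient scores one lower, and no definition rules this out

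*Combined protocol and SAP*

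**What the plan says.** The document is the combined protocol and SAP.

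- **STUDY ENDPOINTS:** "The primary endpoint is the combined total number of insertions or redirection of the needle being used for the procedure". The OBJECTIVES section asks in the same terms: "Is there an identifiable difference in the number of insertions and redirections of the needle for a lumbar neuraxial procedure". The null hypothesis also refers to insertions and redirections.
- **PROCEDURES INVOLVED, Randomization, live scoring in groups 1-3:** after marking, "the research nurse will notify the observer that they may enter the room to observe the procedure and collect the relevant data". The items to be counted are not listed.
- **Same section, video fallback:** "If one of the blinded study observers is not readily available due clinical responsibilities, the research nurse will video record the procedure per protocol". A blinded observer later scores the recording, and the instruction for that scoring is that "the number of redirections and reinsertions will be counted and relayed to the research nurse". This paragraph stands between the procedures for groups 1-3 and those for groups 4-6, and it relies on the research nurse, who appears only in the former.
- **Definitions:** insertion, reinsertion and redirection are not defined anywhere. The document does not say whether the first needle pass is counted.
- **Analysis:** chi-square or Fisher's exact test. The text does not say how a count becomes categories.

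**The concern.** An insertion count includes the first entry of the needle; a reinsertion count, read literally, does not. An uncomplicated first pass would score 1 under the endpoint definition and 0 under the video instruction. The fallback is also the only place that itemises what an observer counts, so the one operational instruction for the primary endpoint does not match the endpoint.

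If live observers follow the endpoint wording and video reviewers follow the fallback wording, identical procedures get scores one unit apart. One unit is large on this scale, because most procedures are expected to need very few passes. With equal video use across arms the result is added noise. With unequal use it would also be bias. The variables listed for collection do not include observation mode, so the offset could not be traced afterwards.

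**Working it through.** **1. The plan's own figure.** Inputs from DATA MANAGEMENT AND CONFIDENTIALITY: first-insertion success 90.1% (VerTouch) and 62.9% (ultrasound), alpha 0.05 (taken as two-sided), power 80%.

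n = [1.960 × √(2 × 0.765 × 0.235) + 0.842 × √(0.901 × 0.099 + 0.629 × 0.371)]² / 0.272² = (1.175 + 0.478)² / 0.0740 ≈ 36.9, so 37 per group. The stated 38 is reproduced to within one patient.

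**2. The offset.** Let I be insertions including the first, and R redirections.
- Endpoint: T = I + R.
- Video score read literally: V = (I − 1) + R.
- T − V = 1 for every patient.

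First-insertion success is I = 1, which is the same event as zero reinsertions. That outcome, and the sample size built on it, do not change.

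**3. Size of one unit (assumed model).** Take the count as 1 + geometric, with the success rates above as the chance of a score of 1. The mean is 1/p: 1/0.901 = 1.11 and 1/0.629 = 1.59, a gap of 0.48. The offset is about twice that gap. The model treats first-insertion success as no further manipulation at all, which the protocol does not say.

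**4. How many patients could be affected.** The accrual table gives 60 pregnant patients; over three arms that is 20 of each arm's 40. The video share f is not stated. At f = 20% of groups 1-3, 0.20 × 20 = 4 of 40, or 10% of an arm. The arm mean falls by 0.10, and the variance rises by about 0.10 × 0.90 = 0.09 if video use is unrelated to the count.

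**5. Rank test (Mann-Whitney, simulated, 40 per arm, VerTouch v ultrasound).**

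| Video share of groups 1-3, both arms | Power |
|---|---|
| 0% | about 87% |
| 20% | about 76% (75 to 76% over repeat runs) |
| 40% | about 66% |

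Part of the loss comes from chance differences between arms in the number of videos.

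**6. Chi-square on a cut at one or fewer (exact enumeration, 40 per arm).** A video patient meets the cut when T ≤ 2, with probability 1 − (1 − p)²: 0.990 for VerTouch and 0.862 for ultrasound. With 10% of each arm on video:
- VerTouch: 0.9 × 0.901 + 0.1 × 0.990 = 0.910.
- Ultrasound: 0.9 × 0.629 + 0.1 × 0.862 = 0.652.

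Power falls from 84.9% to 82.9%, a loss of 2 points.

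**7. Unequal video use (illustration only).** With shares of 10% v 30% of groups 1-3, the spurious difference is 0.20 within those groups and 0.20 / 2 = 0.10 over both cohorts. The rank test's type I error is then about 8%. If ultrasound has the larger share, chi-square power on the same cut is 77.9%.

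**8. If the fallback were also used in groups 4-6.** With 20% of all 40 per arm on video, rank-test power would be about 65% and chi-square power 80.8%. The placement of the paragraph does not support that reach, so these are outer values.

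**The case against.** The strongest reply is that the offset is inferred. It needs a live rule that counts the first pass, and no live rule is written. The fallback wording could be the rule for both modes, or loose wording for insertions; either way the two modes agree. Scoring is limited to three blinded observers, who also review the videos. At least 10 procedures at each site are filmed to check agreement, and a uniform gap of one might show there.

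Much of this stands. A reader might infer that the two modes demonstrably use different rules. The documents do not show that; they show one instruction that conflicts with the endpoint and no definition to settle it. But if all observers followed the fallback wording, the recorded variable would still not be the endpoint as written. The agreement check measures consistency between observers and sets no counting rule.

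A reader might also infer bias against or in favour of one arm, because the SIGNIFICANCE section says that the "additional materials needed to perform the procedure with US take time to gather and further prolong the procedure". That describes ordinary practice. In groups 1-3 both the VerTouch and the ultrasound machine go to every room before the allocation is revealed, so gathering time cannot differ by arm. Longer scanning remains possible, but no duration is given, and the stated trigger is the observer's clinical duties.

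Finally, a rank test is not the planned analysis. The larger power loss above therefore describes an analysis that uses the whole count, not the one named in the plan.

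**Conclusion.** The point holds as a conflict of wording on the primary endpoint: OBJECTIVES and STUDY ENDPOINTS count insertions plus redirections, and the video fallback counts reinsertions plus redirections. Followed literally, the video score is one lower. Whether that happens in practice cannot be told from the documents.

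Its size depends on an unstated video share, an assumed 1 + geometric count and the test used. At 20% of groups 1-3 in each arm, the loss is about 11 points of power (87% to 76%) for a rank test and about 2 points for a chi-square test cut at one or fewer. There is no loss for first-insertion success, and the sample size stands. Bias between arms is conditional on unequal video use, for which there is no documentary basis. Severity is minor to moderate: worth correcting because the primary count should have one meaning, but not a threat to the trial on its own.

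**What to change.** - In the video fallback paragraph, replace the phrase about redirections and reinsertions with: *all skin insertions, including the first, plus all redirections*.
- Define insertion, reinsertion and redirection once, state that an uncomplicated first pass scores 1, and apply the rule to live and video scoring alike.
- Record for each patient whether the count was made live or from video.
- For counts already recorded from video, add 1 only where it is confirmed that the first insertion was left out.

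The cost is one sentence, short definitions and one extra data field. No additional patients or staff are needed, and the sample size calculation does not change.

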All standard procedures for neuraxial procedures will be followed (standard practice) after site determination including time out, skin prep, hemodynamic monitoring, post-procedure instruction etc.

Zoomed in audio-less video of the procedure sight will be collected during at least 10 of the procedures, at each site, for inter-observer variability determination. If the subject has any identifying marks in or near the procedure site or refuses video capture of the procedure no video or images will not be collected in that subject. If the blinded observer is not present and the procedure cannot be recorded for any of the above reasons, the patient will be removed from the study.

Data collected on the VerTouch device will only be associated with the subject number when collected from device for technical evaluation of pressure sensor performance.

If US is used the provider chooses to save an image of the anatomy visualized the research nurse or staff will save that image under the subject number for post-hoc analysis of anatomy identified and image quality achieved.

DATA AND SPECIMEN BANKING

We will collect and data including reason for procedure, type of procedure, any anatomical issues affecting procedure (including but not limited to: scoliosis, positioning, BMI, paralysis), and age. The video/images collected will allow us to compare the observer variability.

SHARING RESULTS WITH PARTICIPANTS

Results will not be shared with participants.

STUDY TIMELINES

The individual will participate in the study for the duration of the procedure, which is usually approximately half an hour. It will take approximately one year to enroll all participants, and approximately 3 months to perform data analysis.

INCLUSION AND EXCLUSION CRITERIA

Inclusion criteria are any adult patients undergoing a neuraxial procedure. Necessary to this is the inclusion of pregnant women who make up a significant fraction of neuraxial procedures.

Exclusion criteria are those patients who do not speak English, have a plastic allergy, or are unable to consent.

Other special populations (individuals who are not yet adults, prisoners, vulnerable populations) will also be excluded.

If it is impossible to take a photograph that does not include identifying marks on the back (i.e. a birthmark or tattoo) the patient will be excluded from the video portion of the study

VULNERABLE POPULATIONS

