Patients can withdraw from the study at any time and their data will be deleted, and in no way will this impact their care since the study explicitly does not affect the standard of care. The study team will notify the PI by secure NM or NU email if a subject withdraws from the study.

RISKS TO PARTICIPANTS

No significant risk to the patient exists with the utilization of the VerTouch device. The materials on the device that come in contact with the patient are similar or the same as those that make up the US probes used in current state. The device is non-invasive and does not generate radiation or any other emission that would affect the patient's skin or underlying tissues.

POTENTIAL BENEFITS TO PARTICIPANTS

While there is no direct benefit to participants, we do hope that this will benefit pregnant and non-pregnant patients in the future who are undergoing neuraxial procedures. Our previous feasibility study did suggest that the use of the VerTouch may represent an improvement on the current gold standard of palpation.

DATA MANAGEMENT AND CONFIDENTIALITY

Based on the feasibility study data collected and published earlier this year at our institution the incidence of first insertion success when utilizing the VerTouch device is 90.1%. Using historical data from studies comparing Ultrasound to Palpation the first insertion success rates are 62.9 and 43.6%, respectively. When utilizing the anticipated incidence of first insertion success for the VerTouch device and Ultrasound to complete a sample size calculation, given Type 1 and Type 2 error are 0.05 and 80%, respectively, each group must contain 38 patients. Therefore, when including the control "palpation" group, the total population needs to be 114 patients. We plan to recruit 120 patients, 40 in each group, to ensure appropriate sample size and allow unknown possible exclusions of recruited patients."

All photographs will be maximally zoomed in. If it is impossible to take a video that does not include identifying marks on the back (i.e. a birthmark or tattoo) no image will be taken. Data will be stored in REDcap using NM password protected computers for data entry.

Data in REDcap is backed up nightly using NM servers which are only accessible to the NM IT administrator. Data in REDcap and pictures/videos will be destroyed 5 years after the completion of the study.

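### Ultrasound images are kept only if the unblinded provider chooses to save one, so the planned post-hoc reading of them rests on an operator-selected set (minor, cheap to correct)

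*Combined protocol and SAP*

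**What the plan says.** The only text on keeping ultrasound images is one sentence in the combined protocol and SAP, under PROCEDURES INVOLVED: "If US is used the provider chooses to save an image of the anatomy visualized the research nurse or staff will save that image". It continues "under the subject number for post-hoc analysis of anatomy identified and image quality achieved". A connecting word appears to be missing after the opening clause. The natural reading is conditional: US is used, and the provider chooses to save an image.

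The document sets no required view, no moment of capture, no quality scale and no reader for these images. It does not ask for a reason when no image is saved, and it gives no denominator for the reading.

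The person making the choice knows the allocation. The Randomization text says "Proceduralists will not be blinded to randomization".

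The images are separate from the main analysis. Under STUDY ENDPOINTS, "The primary endpoint is the combined total number of insertions or redirection of the needle being used for the procedure". Blinded observers count it at the bedside or from video.

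**The concern.** An image that exists only at the operator's discretion is missing for reasons that may relate to what the image would have shown. An operator who saw the landmarks clearly may be more inclined to save a frame. An operator who found unusual or difficult anatomy may also be inclined to save one. In either case the saved images are not a record of the US arm as randomised, and a statement such as 'adequate anatomy was seen in x% of images' would not carry over to that arm.

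The stake is limited to that one descriptive reading. It still deserves attention before enrolment, because the reading is a use the protocol itself announces and an image not saved at the bedside cannot be recovered afterwards.

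**Working it through.** **1. Is image capture made complete anywhere else?** No.
- The rules on identifying marks and refusal (PROCEDURES INVOLVED; DATA MANAGEMENT AND CONFIDENTIALITY) concern video and photographs of the procedure site, not the US screen.
- The blinded observer enters only after the site has been marked, and so does not see the scan.
- No other record of what the scan showed is planned.

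**2. Does the main analysis depend on the images?** No. The document gives no figure for the image reading. Its only sample-size figure is "given Type 1 and Type 2 error are 0.05 and 80%, respectively, each group must contain 38 patients", based on first-insertion success. It states that "the incidence of first insertion success when utilizing the VerTouch device is 90.1"%, against 62.9% for US. As a check, with pooled variance, two-sided and no continuity correction:

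- p̄ = (0.901 + 0.629)/2 = 0.765; difference = 0.272
- n = [1.96·√(2·0.765·0.235) + 0.8416·√(0.901·0.099 + 0.629·0.371)]² / 0.272²
- n = (1.175 + 0.478)² / 0.0740 ≈ 36.9, so 37 per group

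This is one below the stated 38, reading the 80% as power. No image variable enters the calculation, so a change to the image rule leaves it untouched.

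**3. How large could the distortion be?** The US arm is planned at 40 ("We plan to recruit 120 patients, 40 in each group"). Everything else here is assumed. Let q be the true share of adequate scans, a the probability that an adequate scan is saved, and b the probability that an inadequate one is saved.

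Apparent adequacy = qa / [qa + (1 − q)b]

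With q = 70%, there are 28 adequate and 12 inadequate scans:

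| a | b | Adequate saved | Inadequate saved | Total saved | Apparent adequacy |
|---|---|---|---|---|---|
| 100% | 100% | 28 | 12 | 40 | 70% |
| 50% | 50% | 14 | 6 | 20 | 70% |
| 80% | 60% | 22.4 | 7.2 | 29.6 | 75.7% |
| 80% | 40% | 22.4 | 4.8 | 27.2 | 82.4% |
| 90% | 30% | 25.2 | 3.6 | 28.8 | 87.5% |
| 60% | 80% | 16.8 | 9.6 | 26.4 | 63.6% |

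The bias is zero whenever a = b, and not only when every scan is saved. It is upward when a > b and downward when a < b.

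For the three rows with a > b, letting q run from 60% to 80% gives inflation of about 4 to 22 percentage points:
- smallest (q = 80%, a = 80%, b = 60%): 25.6/30.4 = 84.2%, which is 4.2 points above 80%
- largest (q = 60%, a = 90%, b = 30%): 21.6/26.4 = 81.8%, which is 21.8 points above 60%

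**4. What could the saved images alone establish?** Take the fourth row: 27.2 saved, 22.4 of them adequate, 12.8 not saved. Without an assumption about the unsaved scans, the arm's true rate could lie anywhere from 22.4/40 = 56% (none adequate) to (22.4 + 12.8)/40 = 88% (all adequate). The interval is 32 points wide before any sampling error.

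**The case against.** The strongest reply is that nothing inferential depends on these images. They are not an endpoint, they enter no comparison between arms, and the text gives a purpose for storing them without naming a rate, scale or arm-level estimate. That is correct, and it is why the point is minor. It does not remove the point, because the protocol announces the analysis and then lets the operator decide which patients contribute to it.

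Three stronger readings are tempting, and the documents do not support them.

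- A reader might infer that the saved images will flatter the scanning. This is plausible but unstated. Providers might equally save difficult anatomy, which reverses the sign.
- A reader might infer that the images are the trial's check on whether US was delivered properly, so that a poor US result could not be interpreted without them. The plan never gives them that role.
- A reader might infer from SIGNIFICANCE, which says "Unfortunately, not many proceduralist are trained in this modality", that this trial's operators scan poorly. That sentence is background on general practice. The document does not state the trial operators' US training, and saved stills would not supply it.

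The missing connecting word also allows another reading, in which the provider picks an image in every US case. Each US patient would then have an image, although the frame would still be the provider's choice. The conditional reading is the more natural one, and the sentence needs repair under either.

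**Conclusion.** The point holds as a minor one. Followed as written, the rule produces an operator-selected set of images that may misrepresent the US arm. This rests on the conditional reading of the sentence and on the absence of any other capture rule.

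The documents do not determine the direction or size of the bias. The percentages above illustrate assumed saving rates and are not estimates for this trial. The primary endpoint, the chi-squared or Fisher comparison between groups, and the sample size are unaffected.

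**What to change.** Replace the discretionary sentence with a rule along these lines: *for every patient in whom US is used for site identification, at least one image is saved under the subject number when the mark is made, whatever its quality; if no view was obtained, this is recorded as 'not identified'.* Add that the post-hoc reading uses all US-allocated patients as its denominator and is descriptive.

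The cost is one or two sentences in the protocol and one extra saved image or entry per US patient, about 40 in all, on equipment already in use for that arm. No sample-size figure changes.

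The fix has limits. The provider still chooses the plane, and a poor still image cannot by itself separate poor scanning from difficult anatomy. The rule removes selection of patients from the reading and does not turn it into a measure of operator skill.
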